#### **OR**

- Had SD, PR, or CR and stopped trial treatment after completion of 35 administrations (approximately 2 years) of trial treatment for reasons other than disease progression or intolerability

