### **5.2.3 Timing of Dose Administration**

Study treatment in all arms will begin on Day 1 of each 3-week dosing cycle after all procedures/assessments have been completed as detailed on the Trial Flow Chart (Section 6.0). Trial treatments may be administered up to 3 days before or after the scheduled Day 1 of each cycle due to administrative reasons.

All trial treatments may be administered on an outpatient basis.

For subjects randomized to the combination arms treatment will be administered in the order presented below:

- Pembrolizumab or placebo infusion is administered first followed by the cisplatin infusion and then 5-FU infusion (or capecitabine).

Treatment may continue with pembrolizumab+chemotherapy or placebo+chemotherapy until documented confirmed disease progression, unacceptable AE(s), intercurrent illness that prevents further administration of treatment, Investigator's decision to withdraw the subject, subject withdraws consent, pregnancy of the subject, noncompliance with trial treatment or procedure requirements, subject receives 35 administrations (approximately 2 years) of study medication, or administrative reasons requiring cessation of treatment.

Note: Dosing interruptions are permitted in the case of medical / surgical events or logistical reasons (ie elective surgery, unrelated medical events, subject vacation, and holidays) not related to study therapy. Subjects should be placed back on study therapy as soon as clinically appropriate per the investigator, and not exceeding 3 weeks from the interrupted dosing. Day 1 of subsequent cycles should be adjusted accordingly to adhere to every 3-week dosing schedule. Discuss with the Sponsor if subjects cannot restart study medication within 3 weeks. The reason for interruption should be documented in the subject's study record.

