#### **5.2.3.1 Pembrolizumab**

Regardless of clinical benefit, subjects may only receive 35 administrations (approximately 2 years) with study treatment. Pembrolizumab 200 mg fixed dose will be administered as a 30-minute IV infusion Q3W. Sites should make every effort to target infusion timing to be as close to 30 minutes as possible. However, given the variability of infusion pumps from site to site, a window of -5 minutes and +10 minutes is permitted (ie, infusion time is 30 minutes: -5 min/+10 min).

The Pharmacy Manual contains specific instructions for the preparation of the pembrolizumab infusion fluid and administration of infusion solution.

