### **5.8 Subject Withdrawal/Discontinuation Criteria**

#### **5.8.1 Discontinuation of Treatment**

Discontinuation of treatment does not represent withdrawal from the trial.

As certain data on clinical events beyond treatment discontinuation may be important to the study, they must be collected through the subject's last scheduled follow-up, even if the subject has discontinued treatment. Therefore, all subjects who discontinue trial treatment prior to completion of the trial will still continue to participate in the trial as specified in Section 6.0 - Trial Flow Chart and Section 7.1.5.3 – Post-Treatment Visits.

Subjects may discontinue treatment at any time for any reason or be dropped from treatment at the discretion of the investigator should any untoward effect occur. In addition, a subject may be discontinued from treatment by the investigator or the Sponsor if treatment is inappropriate, the trial plan is violated, or for administrative and/or other safety reasons. Specific details regarding procedures to be performed at treatment discontinuation are provided in Section 7.1.4 – Other Procedures.

A subject must be discontinued from treatment but continue to be monitored in the trial for any of the following reasons:

- The subject or subject's legally acceptable representative requests to discontinue treatment.
- Confirmed radiographic disease progression outlined in Section 7.1.5 (exception if the Sponsor approves treatment continuation).
- Unacceptable adverse experiences as described in Section 7.2.

- Any progression or recurrence of any malignancy, or any occurrence of another malignancy that requires active treatment
- Intercurrent illness other than another malignancy as noted above that prevents further administration of treatment
- Recurrent Grade 2 pneumonitis
- A confirmed positive serum pregnancy test
- Noncompliance with trial treatment or procedure requirements
- Investigator's decision to withdraw the subject.
- Completed 35 administrations (approximately 2 years) of treatment.

*Note: 35 administrations of study medication are calculated from the date of first dose. Subjects who stop study medication after 35 administrations may be eligible for up to 17 additional study treatments if they progress after stopping study treatment provided they meet the requirements detailed in Section 7.1.2.6.4.*

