- Discontinuation of treatment may be considered for subjects who have attained a confirmed complete response (CR) and have been treated for at least 8 cycles (at least 24 weeks), receiving 2 cycles of the combination including 2 doses of pembrolizumab and at least 80% of the planned doses of cisplatin, 5-Fluorouracil or capecitabine] beyond the date when the initial CR was declared.

Subjects who stop [pembrolizumab or the combination] with stable disease (SD), partial response (PR), or CR, may be eligible for up to 1 year (17 cycles) of [pembrolizumab or additional combination therapy] if they experience disease progression after stopping [pembrolizumab or combination trial treatment]. This retreatment is termed the Second Course Phase (Retreatment) and is described in detail in Section 5.2.2.

- Administrative reasons

The End of Treatment and Follow-up visit procedures are listed in Section 6.0 (Protocol Flow Chart) and Section 7.1.5 (Visit Requirements). After the end of treatment, each subject will be followed for 30 days for AE monitoring (SAEs and ECIs will be collected for 90 days after the end of treatment or 30 days after the end of treatment if the subject initiates new anticancer therapy, whichever occurs first, as described in Section 7.2.3.1). Subjects who discontinue for reasons other than PD will have post-treatment follow-up for disease status until disease progression, initiating a non-study cancer treatment, withdrawing consent or becoming lost to follow-up. After documented disease progression each subject will be followed by telephone for OS until death, withdrawal of consent, or the end of the study, whichever occurs first.

For subjects who are discontinued from treatment but continue to be monitored in the trial, all visits and procedures, as outlined in the trial flowchart, should be completed.

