### **Progression-free Survival (PFS)**

The non-parametric Kaplan-Meier method will be used to estimate the PFS curve in each treatment group. The treatment difference in PFS will be assessed by the stratified log-rank test. A stratified Cox proportional hazards model with Efron's method of tie handling will be used to assess the magnitude of the treatment difference (ie, hazard ratio) between the treatment arms. The hazard ratio and its 95% confidence interval from the stratified Cox model with Efron's method of tie handling and with a single treatment covariate will be reported. Geographic region, backbone therapy (5-FU or Capecitabine) and disease status will be used as the stratification factors in both the stratified log-rank test and the stratified Cox model.

Since disease progression is assessed periodically, PD can occur any time in the time interval between the last assessment where PD was not documented and the assessment when PD is documented. For the primary analysis, for the subjects who have PD, the true date of disease progression will be approximated by the date of the first assessment at which PD is

objectively documented per RECIST 1.1, regardless of discontinuation of study drug. Death is always considered as a confirmed PD event. Subjects without documented PD/death will be censored at the last disease assessment date.

In order to evaluate the robustness of the primary endpoint PFS per RECIST 1.1 by blinded central radiologists' review, we will perform two sensitivity analyses with a different set of censoring rules. The first sensitivity analysis is the same as the primary analysis except that it censors at the last disease assessment without PD when PD or death is documented after more than one missed disease assessment. The second sensitivity analysis is the same as the primary analysis except that it considers discontinuation of treatment or initiation of an anticancer treatment subsequent to discontinuation of study-specified treatments, whichever occurs later, to be a PD event for subjects without documented PD or death. The censoring rules for primary and sensitivity analyses are summarized in [Table 12](#) below.

**Table 12** Censoring Rules for Primary and Sensitivity Analyses of PFS

Situation	Primary Analysis	Sensitivity Analysis 1	Sensitivity Analysis 2

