No PD and no death; new anticancer treatment is not initiated	Censored at last disease assessment	Censored at last disease assessment	Censored at last disease assessment if still on study therapy; progressed at treatment discontinuation otherwise
No PD and no death; new anticancer treatment is initiated	Censored at last disease assessment before new anticancer treatment	Censored at last disease assessment before new anticancer treatment	Progressed at date of new anticancer treatment
PD or death documented after $\leq 1$ missed disease assessment	Progressed at date of documented PD or death	Progressed at date of documented PD or death	Progressed at date of documented PD or death
PD or death documented after $\geq 2$ missed disease assessments	Progressed at date of documented PD or death	Censored at last disease assessment prior to the $\geq 2$ missed disease assessment	Progressed at date of documented PD or death

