#### PFS:

At the final PFS-PD-L1 CPS1 (H1) analysis (IA2), approximately 16 months after the last subject is randomized approximately 430 PFS events will be accumulated in the combination therapy arm and control arm. With 430 events, the study has ~91% power to detect a hazard ratio of 0.65 (pembrolizumab in combination with SOC vs. SOC) at alpha = 0.10% (one-sided). The sample size calculation is based on the following assumptions: 1) progression-free survival follows an exponential distribution with a median of 6 months in the control arm, 2) an enrollment period of 19 months, and 3) a yearly dropout rate of 5%.

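### PFS Sensitivity Analysis 2 scores subjects who remain progression-free after completing 35 administrations, or after stopping in confirmed CR, as progressed on the day treatment stopped

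*Combined protocol and SAP*

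**What the plan says.** Section 8.6.1 plans two sensitivity analyses of PFS. In the text, SA2 follows the primary analysis except that it "considers discontinuation of treatment or initiation of an anticancer treatment subsequent to discontinuation of study-specified treatments", whichever comes later, as a PD event when neither PD nor death is documented. Table 12 row 1 gives the SA2 rule for subjects without PD, death or new anticancer treatment: "Censored at last disease assessment if still on study therapy; progressed at treatment discontinuation otherwise". The primary analysis and Sensitivity Analysis 1 censor the same subjects at the last disease assessment.

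Elsewhere the protocol treats planned stops as discontinuation:

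- Section 5.8.1 lists "Completed 35 administrations (approximately 2 years) of treatment" among the reasons a subject must be discontinued. The same list allows discontinuation after confirmed CR.
- Section 5.2.3.1 states the limit without regard to outcome: "Regardless of clinical benefit, subjects may only receive 35 administrations (approximately 2 years) with study treatment".
- Section 5.2.3 applies it to both chemotherapy arms, placebo included: treatment may continue until, among other things, the "subject receives 35 administrations (approximately 2 years) of study medication".
- Section 5.2.2 describes completers eligible for a second course as having SD, PR or CR and as having "stopped trial treatment after completion of 35 administrations (approximately 2 years) of trial treatment for reasons other than disease progression or intolerability".
- The Section 6.1 flow charts (footnote b) and Section 7.1.2.6.3 ask for continued imaging, every 6 weeks, in subjects who stop without documented progression.

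**The concern.** Counting a treatment stop as progression is a reasonable stress test when the stop may hide progression, for example after toxicity, clinical decline or withdrawal. A stop fixed by dose count, or made because of a complete response, carries no such signal. These subjects go on being scanned, and SA2 overrides their later progression-free scans.

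The rule also reverses the order of outcomes. Dose 35 falls at about month 23.5. A completer still progression-free at month 35 is scored as progressed at month 23.5, while a completer with documented PD at month 30 is scored at month 30.

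SA2 is one of only two planned robustness checks on the PFS endpoint behind H1. A gap between SA2 and the primary result would be read as sensitivity to censoring, when part of it comes from the 35-administration limit. If the combination works, more of its subjects reach dose 35 event-free, so this part of the gap runs against it and grows with the benefit.

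**Working it through.** **Inputs.** From Section 8.9: 750 subjects randomised 1:1:1 (250 per arm); exponential PFS with control median 6 months; HR 0.65; 19-month enrolment; 5% yearly dropout; final PFS analysis (IA2) 16 months after the last randomisation with about 430 events; one-sided alpha 0.10%. Uniform accrual is an assumption.

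**Rates per month.** Control λc = ln 2/6 = 0.1155. Combination λt = 0.65 × 0.1155 = 0.0751. Dropout η = −ln(0.95)/12 = 0.00427. Follow-up at IA2 runs from 16 to 16 + 19 = 35 months.

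**The plan's own figures.**

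- Power: Φ(√(430/4) × |ln 0.65| − 3.090) = Φ(4.466 − 3.090) = 91.6%. With looks at 389 and 430 events and Hwang-Shih-DeCani spending (gamma −4), the nominal p-values are 0.0007 and 0.0007, as in Table 15, and power is 90.9%. The plan states about 91%.
- Expected events per arm: 250 × λ/(λ+η) × [1 − mean of exp(−(λ+η)u) for u from 16 to 35]. This gives 227.1 control + 202.2 combination = 429, against about 430 in the plan.
- Event-free and in follow-up at the cut: 14.5 control + 36.3 combination = 50.8.

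**Time of dose 35.** 34 intervals × 21 days = 714 days = 23.46 months. A share of (35 − 23.46)/19 = 61% of subjects enrol early enough to reach it by IA2.

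**False events if every event-free subject stays on treatment to dose 35 (upper bound).** Count per arm = (250/19) × ∫ exp(−(λ+η)u) du from 23.46 to 35:

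| | Control | Combination |
|---|---|---|
| At risk at 23.46 months | 9.1 | 23.6 |
| Scored as progressed by SA2 | 5.0 | 15.5 |

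That is 20.5 of the 50.8 subjects still event-free and in follow-up (40%).

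**Effect on the curve.** PFS just after month 23.46 = S(23.46) × (1 − f × flagged/at risk), where f is the share of event-free subjects who stay on treatment to dose 35:

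| | Combination | Control | Difference (points) |
|---|---|---|---|
| No rescoring | 17.2% | 6.7% | 10.5 |
| f = 1 | 5.9% | 3.0% | 2.9 |
| f = 0.5 | 11.5% | 4.8% | 6.7 |

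At f = 0.5 the false events are 7.7 and 2.5.

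**Effect on the hazard ratio** (1,500 simulated trials per scenario, unstratified Cox, Efron ties):

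- True HR 0.65, f = 1: 0.648 to 0.670.
- True HR 0.65, f = 0.5: 0.650 to 0.659.
- True HR 1: 1.002 to 1.003.

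A second simulation with Breslow ties gave 0.649 to 0.670 at f = 1, 0.651 to 0.660 at f = 0.5 and 0.652 to 0.656 at f = 0.25. Events at f = 1 rose from about 429 to about 450.

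**Dependence on the true effect (f = 1).** Combination versus control false events are 15.5 versus 5.0 at HR 0.65, 9.5 versus 5.0 at HR 0.8, and 5.0 versus 5.0 at HR 1.

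**CR stops.** The documents give no CR rate. Purely as an illustration, if a quarter of event-free subjects followed beyond month 12 had stopped in CR at month 12, in addition to all completers, the SA2 HR would be about 0.69.

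**Who is not affected.** Subjects with documented PD, death or new anticancer treatment are dated by rows 2 to 4 of Table 12.

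**The case against.** The case for leaving SA2 alone has several parts.

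*Small effect.* SA2 carries no alpha. At the upper bound the shift is ln(0.670/0.648) = 0.033 on the log scale, against a standard error of about 2/√430 = 0.096, or about 0.35 standard errors. An SA2 estimate of 0.67 still lies below the IA2 boundary of 0.735 in Table 15, and at HR 1 the rule creates no spurious benefit. All of this stands, and it limits the importance of the point.

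*Fragile curve figures.* The fall from 10.5 to 2.9 points needs every subject to reach dose 35 on the same day, with about 24 and 9 at risk, and no planned analysis uses PFS at that time. Dose interruptions would delay and spread the drop. If dose 35 fell at month 25 or 26 (an assumption), the flagged counts would be 12.5 and 3.8, or 10.7 and 3.2. This also stands, and the hazard ratio is the better summary.

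*Unknown net direction.* Section 5.2.1.2 lets subjects on pembrolizumab continue it alone after stopping chemotherapy for adverse events, while placebo subjects may stop study treatment. SA2 would count those controls as events. The direction of the whole gap between SA2 and the primary analysis is therefore not established; only the completer component is sized here.

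*Design intent.* SA2 is meant to count stopping without PD as an event, and it scores stops for toxicity, pregnancy or administrative reasons the same way. Where to draw the line is partly a choice. But for completers the protocol has already drawn it: Section 5.2.2 says they stopped for reasons other than progression or intolerability.

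None of this supplies an exemption. Section 8.6.1 reserves the supplemental SAP for exploratory methods, and Table 13 refers back to Table 12.

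**Conclusion.** The concern holds. As written, SA2 records progression for subjects whom the protocol itself describes as stopping for other reasons and who are still being imaged. At the design effect the completer component adds up to about 20 false events at IA2, roughly three to one in the combination arm, and moves the SA2 hazard ratio by about 0.01 (half staying on treatment) to 0.02 (all staying on treatment). These figures rest on uniform accrual, exponential PFS, dosing on schedule and an equal share staying on treatment in both arms; the documents give no rate of reaching dose 35. Stops in CR would add an amount that cannot be sized. The primary PFS analysis and the H1 test, alpha and power are untouched. This should be corrected because it blurs what SA2 is meant to show; it does not threaten the trial's conclusions.

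**What to change.** Before unblinding, make two edits in Section 8.6.1.

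1. Table 12, SA2, row 1: after the clause on subjects still on study therapy, add *or if treatment stopped because 35 administrations were completed or because of confirmed CR*, and restrict the progressed outcome to stops *for any other reason*.
2. SA2 sentence in the text: qualify discontinuation of treatment with *for reasons other than completion of 35 administrations or confirmed CR*.

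Section 8.0 allows changes to non-confirmatory analyses to be documented in the supplemental SAP before unblinding. That may be a lighter route if the sponsor regards SA2 as non-confirmatory.

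The drafting cost is one cell and one sentence, and no treatment rule changes. The downside is that SA2 event status would depend on the recorded reason for stopping, including an investigator-determined CR, in a check on a centrally reviewed endpoint. Section 8.6.4.1 plans to display the primary reason for discontinuation but does not say whether this means treatment or trial. The treatment-level reason must therefore be confirmed as an analysis variable.

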**Overall Survival (OS)**

The non-parametric Kaplan-Meier method will be used to estimate the survival curves. The treatment difference in survival will be assessed by the stratified log-rank test for superiority hypotheses. A stratified Cox proportional hazards model with Efron's method of tie handling will be used to assess the magnitude of the treatment difference (ie, the hazard ratio). The hazard ratio and its 95% confidence interval from the stratified Cox model with a single treatment covariate will be reported. Geographic region, backbone therapy (5-FU or

Capecitabine) and disease status will be used as the stratification factors in both the stratified log-rank test and the stratified Cox model.

The non-inferiority hypothesis (H4) for pembrolizumab monotherapy vs. SOC will be evaluated using a stratified Cox regression model. The statistical criterion for the success of hypothesis H4 is that, if the upper bound of the confidence interval, based on the alpha level allocated to the analysis, for the hazard ratio (HR: monotherapy arm vs. control) is < 1.2, the pembrolizumab monotherapy arm could be considered as non-inferior to the control arm in terms of OS.

**Overall Response Rate (ORR)**

Stratified Miettinen and Nurminen’s method with strata weighting by sample size will be used for comparison of the ORR between the treatment groups. Geographic region, backbone therapy (5-FU or Capecitabine) and disease status will be used as the stratification factors in the analysis.

Table 13 summarizes the primary analysis approach for primary and secondary efficacy endpoints. Sensitivity analysis methods are described above for each endpoint.

Table 13 Analysis Strategy for Key Efficacy Endpoints

Endpoint/Variable (Description, Time Point)	Statistical Method†	Analysis Population	Missing Data Approach
Primary Endpoints			
PFS per RECIST 1.1 by blinded central radiologists’ review	Testing: Stratified Log-rank test. Estimation: Stratified Cox model with Efron's tie handling method	ITT	
 
• Primary censoring rule
 
• Sensitivity analysis 1
 
• Sensitivity analysis 2 (More details in Table 12)
 

OS	Testing: Stratified Log-rank test Estimation: Stratified Cox model with Efron's tie handling method	ITT	Censored at last date known alive
Secondary Endpoint			
ORR Per RECIST 1.1 by blinded central radiologists’ review	Stratified Miettinen and Nurminen method	ITT	Subjects with missing data are considered non-responders
† Statistical models are described in further detail in the text. For stratified analyses, Geographic region, backbone therapy and disease status will be used as the stratification factors in both the stratified log-rank test and the stratified Cox model.			

## 8.6.2 Statistical Methods for Safety Analyses

Safety and tolerability will be assessed by clinical review of all relevant parameters including adverse experiences (AEs), laboratory tests, vital signs, etc.

The analysis of safety results will follow a tiered approach (Table 14). The tiers differ with respect to the analyses that will be performed. Safety parameters or adverse experiences of special interest that are identified *a priori* constitute “Tier 1” safety endpoints that will be subject to inferential testing for statistical significance with p-values and 95% confidence intervals provided for between-group comparisons. Other safety parameters will be considered Tier 2 or Tier 3. Tier 2 parameters will be assessed via point estimates with 95% confidence intervals provided for between-group comparisons; only point estimates by treatment group are provided for Tier 3 safety parameters.

Adverse experiences (specific terms as well as system organ class terms) and predefined limits of change in laboratory, vital signs, and ECG parameters that are not pre-specified as Tier-1 endpoints will be classified as belonging to "Tier 2" or "Tier 3", based on the number of events observed. Membership in Tier 2 requires that at least 4 subjects in any treatment group exhibit the event; all other adverse experiences and predefined limits of change will belong to Tier 3.

The threshold of at least 4 events was chosen because the 95% confidence interval for the between-group difference in percent incidence will always include zero when treatment groups of equal size each have less than 4 events and thus would add little to the interpretation of potentially meaningful differences. Because many 95% confidence intervals may be provided without adjustment for multiplicity, the confidence intervals should be regarded as a helpful descriptive measure to be used in review, not a formal method for assessing the statistical significance of the between-group differences in adverse experiences and predefined limits of change.

Continuous measures such as changes from baseline in laboratory, vital signs, and ECG parameters that are not pre-specified as Tier-1 endpoints will be considered Tier 3 safety parameters. Summary statistics for baseline, on-treatment, and change from baseline values will be provided by treatment group in table format.

Based on a review of historic chemotherapy data and data from ongoing pembrolizumab clinical trials in gastric cancer, there are no AEs of interest that warrant inferential testing for comparison between treatment arms in this study. Therefore, there are no Tier I events in this study. The broad clinical and laboratory AE categories consisting of the percentage of subjects with any AE, any drug related AE, any serious AE, any Grade 3-5 AE, an AE which is both Grade 3-5 and drug-related, an AE which is both drug-related and serious, dose modification due to AE, and who discontinued due to an AE, and death will be considered Tier 2 endpoints. Ninety Five percent (95%) confidence intervals Tier 2) will be provided for between-treatment differences in the percentage of subjects with events; these analyses will be performed using the Miettinen and Nurminen method (1985), an unconditional, asymptotic method.

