All adverse events that occur after the consent form is signed but before randomization/treatment allocation must be reported by the investigator if they cause the subject to be excluded from the trial, or are the result of a protocol-specified intervention, including but not limited to washout or discontinuation of usual therapy, diet, placebo treatment or a procedure. From the time of randomization/treatment allocation through 30 days following cessation of treatment, all adverse events must be reported by the investigator. Such events will be recorded at each examination on the Adverse Event case report forms/worksheets. The reporting timeframe for adverse events meeting any serious criteria is described in section 7.2.3.1. The investigator will make every attempt to follow all subjects with non-serious adverse events for outcome.

Electronic reporting procedures can be found in the EDC data entry guidelines. Paper reporting procedures can be found in the Investigator Trial File Binder (or equivalent).

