### **7.2.3 Immediate Reporting of Adverse Events to the Sponsor**

#### **7.2.3.1 Serious Adverse Events**

A serious adverse event is any adverse event occurring at any dose or during any use of Sponsor's product that:

- Results in death;
- Is life threatening;
- Results in persistent or significant disability/incapacity;
- Results in or prolongs an existing inpatient hospitalization;
- Is a congenital anomaly/birth defect;
- Is an other important medical event

**Note:** In addition to the above criteria, adverse events meeting either of the below criteria, although not serious per ICH definition, are reportable to the Sponsor in the same timeframe as SAEs to meet certain local requirements. Therefore, these events are considered serious by the Sponsor for collection purposes.

- Is a cancer;
- Is associated with an overdose.

Refer to [Table 11](#) for additional details regarding each of the above criteria.

For the time period beginning when the consent form is signed until randomization/treatment allocation, any serious adverse event, or follow up to a serious adverse event, including death due to any cause other than progression of the cancer under study (reference Section 7.2.3.3 for additional details), that occurs to any subject must be reported within 24 hours to the Sponsor if it causes the subject to be excluded from the trial, or is the result of a protocol-specified intervention, including but not limited to washout or discontinuation of usual therapy, diet, placebo treatment or a procedure.

For the time period beginning at randomization/treatment allocation through 90 days following cessation of treatment, or 30 days following cessation of treatment if the subject initiates new anticancer therapy, whichever is earlier, any serious adverse event, or follow up to a serious adverse event, including death due to any cause other than progression of the cancer under study (reference Section 7.2.3.3 for additional details), whether or not related to the Sponsor's product, must be reported within 24 hours to the Sponsor either by electronic media or paper. Electronic reporting procedures can be found in the EDC data entry guidelines. Paper reporting procedures can be found in the Investigator Trial File Binder (or equivalent).

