### **8.12 EXTENT OF EXPOSURE**

The extent of exposure will be summarized as duration of treatment in cycles.

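### Tier 2 adverse events are compared only as crude percentages although the collection window follows treatment length; exposure-adjusted and time-to-first-event estimates should be added alongside.

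*Combined protocol and SAP*

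**What the plan says.** Section 8.6.2 gives 95% Miettinen-Nurminen intervals for "between-treatment differences in the percentage of subjects with events" in the Tier 2 categories. Table 14 lists an interval and descriptive statistics for each category and nothing else. There are no Tier 1 events and no safety p-values.

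The collection window is set by the end of treatment. Section 7.2 says: "From the time of randomization/treatment allocation through 30 days following cessation of treatment, all adverse events must be reported by the investigator". Section 7.2.3.1 gives serious events a longer window: "For the time period beginning at randomization/treatment allocation through 90 days following cessation of treatment, or 30 days following cessation of treatment" if new anticancer therapy begins, whichever is earlier. Section 7.2.3.2 uses the same window for events of clinical interest.

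Treatment length is tied to disease control. Section 5.2.3 says: "Treatment may continue with pembrolizumab+chemotherapy or placebo+chemotherapy until documented confirmed disease progression", with other stopping reasons and a limit of 35 administrations.

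Exposure is reported separately. Section 8.12 reads in full: "The extent of exposure will be summarized as duration of treatment in cycles". No section connects that summary to event counts, and no exposure-adjusted, fixed-window or time-to-first-event safety analysis is planned.

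**The concern.** A crude percentage depends on how toxic a regimen is and on how long each subject is observed. Here observation time is itself an outcome of treatment: an arm that delays progression is treated for longer and has more time to record a first event. Two arms with the same monthly event risk can then show different percentages, and the planned interval cannot separate toxicity from duration. Safety and tolerability is a stated secondary objective (Section 3.2), and these intervals are the only between-arm safety estimates planned. The distortion grows with the efficacy that the trial hopes to show.

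**Working it through.** **Inputs from the documents**
- Section 8.9 (PFS): "progression-free survival follows an exponential distribution with a median of 6 months in the control arm"; HR 0.65; 430 events; one-sided alpha 0.10%; 19 months' enrolment; 5% yearly dropout; final PFS analysis 16 months after the last randomization.
- Section 8.9: about 750 subjects at 1:1:1, so about 250 per arm.
- Section 5.2.3.1: at most 35 administrations. 35 × 21 days / 30.4375 = 24.15 months.
- Sections 7.2 and 7.2.3.1: tails of 30 days (0.99 month) and 90 days (2.96 months).

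**Assumptions**
- Treatment ends at the PFS event or the cap.
- The first-event hazard is constant and identical in both arms, at illustrative values.
- Death does not shorten the tail.

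**Step 1: the plan's own figure.** Power = Φ(√430/2 × |ln 0.65| − 3.09) = 0.916, against the stated 91% or so. Exponential PFS with the stated accrual, follow-up and dropout gives 227 + 202 = 429 events, against about 430. The PFS assumptions reproduce.

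**Step 2: treatment and observation time.** Progression hazards are μ = ln 2/6 = 0.1155 per month in control and 0.65 × 0.1155 = 0.0751 in the combination arm (median 6/0.65 = 9.23 months). Mean treatment time under the cap is (1 − exp(−24.15μ))/μ:

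| | Control (months) | Combination (months) | Ratio |
|---|---|---|---|
| Treatment | 8.1 | 11.1 | 1.37 |
| Observed, 30-day tail | 9.1 | 12.1 | 1.33 |
| Observed, 90-day tail | 11.1 | 14.1 | 1.27 |

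**Step 3: crude incidence with the same hazard λ in both arms.** With tail g and cap C = 24.15,

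P(event) = 1 − exp(−λg) × [μ/(μ+λ) × (1 − exp(−(μ+λ)C)) + exp(−(μ+λ)C)].

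At λ = 0.05 with the 30-day tail:
- Control: 1 − 0.952 × [0.698 × 0.982 + 0.018] = 33.0%.
- Combination: 1 − 0.952 × [0.600 × 0.951 + 0.049] = 41.0%.

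The last column is the chance that a two-sided 95% interval excludes zero with 250 per arm (normal approximation):

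| λ per month | Tail | Control | Combination | Excludes zero |
|---|---|---|---|---|
| 0.02 | 30 d | 15.9% | 20.5% | 27% |
| 0.05 | 30 d | 33.0% | 41.0% | 45% |
| 0.10 | 30 d | 51.2% | 60.4% | 54% |
| 0.50 | 30 d | 88.5% | 92.0% | 26% |
| 1.00 | 30 d | 96.1% | 97.4% | 12% |
| 0.05 | 90 d | 39.3% | 46.5% | 37% |
| 0.10 | 90 d | 59.9% | 67.5% | 42% |

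A simulation of 5,000 trials with the Miettinen-Nurminen statistic gave 26%, 46% and 54% for the first three rows, almost always against the combination. With an extra stopping hazard of 0.04 per month in both arms, λ = 0.10 and the 30-day tail, incidence is 44.8% versus 51.3% and the interval excludes zero in 31% of trials.

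**Step 4: the remedy on the same simulated data.** First-event rates per unit of time at risk gave a mean ratio of 1.00, and the interval excluded 1 in 4% to 5% of trials.

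**Step 5: the remedy when the hazard is not constant.** Take identical front-loaded hazards (assumed 0.2 per month for 4 months, then 0.02). Crude incidence is about 54% versus 58%, and the interval excludes zero against the combination in about 13% of trials. The exposure-adjusted ratio is about 0.86, and its interval excludes 1 in about 30% of trials, this time falsely favouring the combination.

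**The case against.** Four points can be made for the plan as it stands.

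**The intervals are descriptive.** Section 8.6.2 says that "the confidence intervals should be regarded as a helpful descriptive measure to be used in review, not a formal method". This stands as far as testing goes: no error rate is inflated. But the reason that section gives for the label is unadjusted multiplicity, which is a different matter from unequal observation time, and the intervals are still meant for use in review.

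**The size rests on assumptions.** A reader might infer that the plan expects treatment to last about 1.5 times longer in the combination arm. It does not say so: 1/0.65 = 1.54 is a ratio of median PFS under the powering alternative. The cap brings the ratio of mean treatment time down to 1.37, and stopping for toxicity, withdrawal or other reasons would lower it further. Some rules could widen the gap: Section 5.2.1.2 lets pembrolizumab subjects continue on pembrolizumab alone after chemotherapy, while placebo subjects may stop study treatment. The documents put no figure on this. Section 8.9 also gives no PFS assumption for monotherapy, so nothing can be quantified for that arm.

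**Chemotherapy toxicity may come early.** Cisplatin may be capped at 6 cycles (Section 5.2.3.3). For early events the crude comparison is distorted much less, as Step 5 shows. This stands.

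**Crude incidence answers a real question,** namely the risk of an event on the regimen as given. This also stands. A reader might infer that safety conclusions should rest on exposure-adjusted rates instead; Step 5 shows why that would exchange one distortion for another.

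**Conclusion.** The point holds as a cheap improvement to the safety analysis. The planned Tier 2 comparison mixes toxicity with length of observation, and nothing else in the plan separates them. Under the PFS alternative used as a proxy for treatment time, identical constant hazards give a spurious excess of about 5 to 9 percentage points in the combination arm for hazards of 0.02 to 0.10 per month. It is smaller with the 90-day window, with added stopping for other reasons, and for rare, near-universal or early-onset events.

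These figures depend on the assumed hazards, on treatment ending at progression or the cap, and on the PFS alternative being true. If PFS did not differ between the arms, this source of imbalance would disappear. A reader might infer that the plan will produce a false safety finding. The documents do not support that: they give no adverse event rate or treatment duration, the distortion is a matter of probability and varies by category, and the intervals carry no formal inference. No efficacy hypothesis or alpha is affected.

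**What to change.** In Section 8.6.2 and Table 14, keep the crude percentages and add beside them:

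1. Exposure-adjusted first-event rates for the Tier 2 adverse event categories, with between-arm 95% intervals. Time at risk should run to the first event or the end of the collection window: 30 days after treatment for adverse events, and 90 days (30 if new anticancer therapy starts) for serious events.
2. Time-to-first-event (cumulative incidence) estimates with death as a competing event, for events concentrated early in treatment.

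State that the crude and exposure-adjusted results are to be read together, and that the simple rate assumes a constant hazard and can falsely favour the longer-treated arm when toxicity is front-loaded.

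The cost is extra tables and programming. Event start dates (Table 11) and treatment duration (Section 8.12) are already collected, so no new data are needed.
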